9.2 Withdrawal of Participants from the Study

A participant may be withdrawn from the study at any time if the participant or the investigator feels that it is not in the participant's best interest to continue.

All participants are free to withdraw from participation at any time, for any reason, specified or unspecified, and without prejudice.

9.3 Replacement of Participants

Participants who withdraw from the study will be replaced.

10 STATISTICAL METHODS AND CONSIDERATIONS

10.1 Sample Size and Randomization

Based on the frequencies that cardiac ectopy observed among 100 healthy individuals during a study examining acute effects on and off coffee, we estimate that, using a two-tailed alpha of 0.05, we will have 80% power in intention-to-treat analyses comparing nights on and off HGNS to detect a 2% increase in cardiac ectopy—meaning, we believe 100 participants will provide adequate power to test our hypothesis.

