PARTICIPANT SELECTION CRITERIA	 Inclusion Criteria: Age 21 years or older Have a hypoglossal nerve stimulation (HGNS) device implanted for obstructive sleep apnea and followed up at UCSF Are willing to abstain from using the HGNS device for no more than two consecutive days as instructed over the 14-day trial period Able and willing to provide written informed consent Exclusion Criteria: Currently pregnant or trying to get pregnant Are currently taking Class 1 or 3 anti-arrhythmic medications Have a history of permanent AF or expected to have AF throughout the study period 				

Version #: 1.1 Version Date: 03 June 2025 Page 6 of 21

	 Have congenital heart disease Are >40% ventricular paced Are unable to read or sign to provide informed consent 				
STUDY DURATION	Participants will participate for approximately 2 weeks. • Randomization and monitoring: up to 2 weeks.				
PROCEDURE	After being fitted with an automatically recording electrocardiographic monitor, the HGNS device will then be "on" versus "off" (where "off" is turning off the HGNS device for one night and "on" is turning on the HGNS device) over the ensuing 14 days. Participants will be randomized to "off-on" versus "on-off" periods, assuring no more than two consecutive days of either device use or not. Electrocardiographic monitoring data will be used to assess for endpoints.				
PRIMARY ENDPOINT	The daily number of cardiac ectopic beats				
SECONDARY ENDPOINTS	 The daily number of PACs The daily number of PVCs The daily presence versus absence of AF episodes ≥ 30 seconds 				
STATISTICS Primary Analysis Plan	Our primary analyses will employ intention-to-treat principles, examining randomization assignment as the primary predictor.				
Rationale for Number of Participants	Using a two-tailed alpha of 0.05, we estimate we will need 100 participants to have 80% power in intention-to-treat analyses comparing nights on and off HGNS to detect a 2% increase in cardiac ectopy.				

Version #: 1.1 Version Date: 03 June 2025 Page 7 of 21

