This will be the first randomized case-crossover assessment to reveal immediate relationships between sleep disruption and more frequent clinically relevant common cardiac arrhythmias pertinent to and potentially including AF episodes. Specifically, premature atrial contractions (PACs) are the most potent predictor of AF. ¹⁶⁻¹⁸ Other potentially important arrhythmias are premature ventricular contractions (PVCs), a higher frequency of which is clinically relevant as it predicts future heart failure. ^{19, 20} Because everyone experiences PACs and PVCs, use of continuously worn ECG monitors that quantify such common ectopy can be used to harness sufficient power to evaluate clinically relevant outcomes as done in the Coffee and Real-time Atrial and Ventricular Ectopy (CRAVE) study. ²¹

Compelling evidence of the direct impact of sleep disruption on discrete AF episodes would be directly and immediately relevant to clinical care of our patients. In fact, identifying near-term triggers of AF is a high priority for patients with AF and may effectively determine lifestyle modifications that can meaningfully affect the risk of an arrhythmia occurrence. 8, 10, 22

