4 CRITERIA FOR EVALUATION

4.1 Primary Endpoint

The daily number of ectopic beats (per 24-hour period).

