7.8 Randomization and Monitoring (Day 1-14)

At 08:00 AM on the first day (Day 1), the participant will receive a text or push notification from a mobile app or text messaging service with instructions for the same day's randomization. Their first reminder regarding their randomization will be at 08:00 PM on Day 1. During the study (Day 1-14), participants will receive two text or push notifications (AM and PM) each day:

- 1. 08:00 AM: Instructions on the present day's randomization, in addition to daily surveys on randomization compliance and sleep quality.
- 2. 08:00 PM: Reminder of instructions on the present day's randomization.

At 08:00 AM on Day 15 participants will complete the final compliance survey and will be reminded to resume their normal HGNS use.

"On" day messages will instruct participants to use their HGNS device and on "off" days, participants will be instructed to not used them. To avoid >2 consecutive days with or without using their device, participants will be randomized in pairs of either "off one day and on the next day" or "on one day and off the next day".

Each participant will also undergo two consecutive days of home sleep apnea recording using the WatchPAT® ONE-M Home Sleep Apnea Test, ideally during the first days of participation.

Throughout the study period (Day 1-14), the participants should continuously wear their ECG monitor.

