10.2 Statistical Analysis Plan (SAP) and Outcome Assessment

Our primary analyses will employ intention-to-treat principles, examining randomization assignment as the primary predictor. Secondary analyses will examine "per-protocol" compliance, which will also allow for quantitative assessments of outcomes per the number of hours off hypoglossal stimulation as the predictor. We will employ logistic regression with robust standard errors (to take clustering within individuals into account) for the dichotomous presence or absence of outcomes (such as at least one daily PAC, PVC, or episode of AF), and a negative binomial model to assess number of daily events.

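### Section 10.2 gives the allowance for within-person clustering only to the logistic models; run as written, the negative binomial model for the primary daily count would give too wide an interval, and the power statement has no stated basis

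*Protocol*

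**What the plan says.** The primary endpoint (protocol section 4.1) is a 24-hour count of ectopic beats. Assignment changes within each person over 14 days: under section 7.8 "participants will be randomized in pairs of either" off-then-on or on-then-off days, so each person contributes seven days of each kind.

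The sample size rests on one statement. The synopsis says "we estimate we will need 100 participants to have 80% power in intention-to-treat analyses" for a 2% increase, and section 10.1 says "we will have 80% power in intention-to-treat analyses comparing nights on and off HGNS to detect a 2% increase in cardiac ectopy". The only source named is the ectopy frequency in a coffee study of 100 healthy people. No mean, variance, dispersion, correlation or model is given.

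Section 10.2 names two models in one sentence. For yes/no outcomes it is "logistic regression with robust standard errors (to take clustering within individuals into account) for the dichotomous presence or absence of outcomes". For counts it is "and a negative binomial model to assess number of daily events". The second clause, which covers the primary endpoint, mentions no participant term, clustering or pairing, and no other section supplies one.

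**The concern.** The design draws its precision from each person being his or her own control. A negative binomial model with assignment as its only term does not use that. Differences between people in their usual ectopy count go into the dispersion parameter and inflate the standard error of the on/off contrast, although assignment is balanced within every person.

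What is at stake is the primary confidence interval as well as the power sentence. If people differ much in usual ectopy, a real small increase would be reported as no effect. Adding a participant term only after the data are seen would be a post hoc change to the primary model.

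**Working it through.** **Inputs from the protocol.** Two-sided alpha 0.05, power 80%, 100 participants, seven on-days and seven off-days each, so 700 and 700 person-days if complete. The 2% is read as relative (the text does not say): ln(1.02) = 0.0198.

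**Assumptions, because the protocol gives no value.** Between-person CV (CVb), within-person day-to-day CV (CVw), a mean of 1,000 beats/day, independent days, full adherence, complete days.

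**1. The plan's own figure.** It cannot be reproduced without a mean or variance, so it is solved backwards.
- Standard error needed: 0.0198/(1.960 + 0.842) = 0.00707.
- For 700 against 700 days, SE = CV x sqrt(2/700) = CV/sqrt(350).
- Largest CV allowed: 0.00707 x sqrt(350) = 13.2%, Poisson noise included. Poisson noise alone then needs a mean of at least 1/0.0175 = 57 beats/day.

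**2. Count model as written.** The CV in step 1 is then taken over all person-days of all people: total CV^2 = (1 + CVb^2)(1 + CVw^2) - 1. The estimate itself varies less than the model believes, with true SD = CVw x sqrt((1 + CVb^2)/350), so

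power = Phi((0.0198 - 1.96 x SE_model)/SD_true).

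Example, CVw 10% and CVb 30%, Poisson noise left out:
- total CV^2 = 1.09 x 1.01 - 1 = 0.1009
- SE_model = sqrt(0.1009/350) = 0.0170
- SD_true = 0.10 x sqrt(1.09/350) = 0.0056
- power = Phi((0.0198 - 0.0333)/0.0056) = about 0.8%

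The same formula gives 82%, 25% and 0% at CVb 10%, 20% and 50%.

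**3. Simulation of the model as written.** 500 trials per setting, 100 people x 7 randomized day pairs, lognormal person means, maximum-likelihood dispersion, CVw 10%:

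| CVb | Power for a true 2% | 95% CI half-width (log scale) |
|---|---|---|
| 0% | 96% | 1.1% |
| 10% | 83% | 1.5% |
| 20% | 28% | 2.3% |
| 30% | 1% | 3.2% |
| 50% | 0% | 4.9% |
| 100% | 0% | 8.3% |

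A within-person analysis of the same data has 93 to 96% power and a half-width of 1.1 to 1.2% throughout. The ratios of widths are therefore about 2.9, 4.4 and 7.2 at CVb 30%, 50% and 100%. At CVw 30% they fall to about 1.4, 1.8 and 2.8, and at CVw 50% to about 1.1, 1.4 and 1.9.

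The formula in step 2 is not a lower bound on the width. At CVb 50% and 100% it gives half-widths of 1.96 x sqrt(0.2625/350) = 5.4% and 1.96 x sqrt(1.02/350) = 10.6%, above the simulated values, because the maximum-likelihood dispersion falls below CV^2 for lognormal person means. The simulated figures are the ones used.

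**4. How exact the 13% limit is.** It is exact when people do not differ. It loosens when part of the spread is between people: at CVw 10% and CVb 10%, total CV = sqrt(0.0201) = 14.2% and power is still 82 to 83%. In the extreme of no within-person variation it is 0.0198 x sqrt(350)/1.96 = 18.9%.

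**5. Direction.** At a true ratio of 1.00 and CVw 10%, the model as written rejected in 0 of 400 trials at CVb 30% and again at 100%. At CVw 50% it rejected in 2 to 3%. The error is conservative.

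**6. With a participant term.** Only CVw counts, and 80% power needs CVw of at most 13.2%. At CVw 20%, 30% and 50%, SE = CVw/sqrt(350) = 0.0107, 0.0160 and 0.0267, and power = Phi(0.0198/SE - 1.96) = 46%, 23% and 11%. Positive correlation between adjacent days relaxes the limit: 13.2%/sqrt(1 - 0.5) = 18.7% at correlation 0.5.

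**7. Clustered errors without a participant term.** At CVw about 13.2% and between-person log-SD 0.5 to 1.5 (100 trials per setting), power was 54 to 75%, against 73 to 85% with person effects and 0% for the model as written.

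**The case against.** The best reply is that silence is not a specification. Section 10.2 names a model family in one clause and never says that it is pooled or uses model-based errors. The same sentence shows that the authors know days cluster within people, and the design is built on within-person comparison. The variance estimator of a count model is often left to a separate analysis plan, which is not at hand. Clustering may well have been meant for both models. That reading is fair, and it is why this is a matter of stating the model and not a proven design failure. It does not remove the point: the protocol does state the correction, attaches it to the yes/no outcomes, and leaves the primary endpoint without it.

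A second reply is that nothing shows people differ enough to matter. The protocol indeed gives no between-person spread. It plans outcomes "such as at least one daily PAC, PVC, or episode of AF", which are informative only if some days have none, and says of PVCs "a higher frequency of which is clinically relevant as it predicts future heart failure". Both hints are weak. The first concerns components of the primary count, and zero days can arise within one person; the second gives no spread. A wide spread is plausible but not documented.

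Three stronger conclusions are tempting and unsupported:
- That the 80% claim is false, or that the model as written cannot deliver it. Section 10.1 names no model or variance, and the model as written has 96% and 83% power at CVb 0% and 10% when CVw is 10%.
- That ignoring clustering here inflates false positives. Because assignment varies within person, it does the reverse.
- That a participant term by itself secures 80% power. Step 6 shows that it does not.

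**Conclusion.** The concern holds as a conditional one. If the primary count model is run as section 10.2 words it, the interval is too wide and a small true effect is likely to be missed. The loss is severe if people differ much in usual ectopy while each person is stable from day to day, and modest if day-to-day variation is itself large: the width ratio ranges from 7.2 down to 1.1 over the settings examined. The model as written has 80% power for 2% only if the CV over all person-days is about 13%, or somewhat more when part of that spread is between people.

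The power statement can be neither confirmed nor refuted from the document. It needs small day-to-day variation under any analysis. All sizes rest on assumed CVs, a relative reading of the 2%, independent and complete days, and full adherence. The point should be fixed before the data are analysed, but it is not evidence that the trial is too small.

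**What to change.** In section 10.2, state that the negative binomial model for daily counts includes a participant term, for example a random intercept, with standard errors clustered on participant. If clustering was already meant for both models, say so; clustered errors alone correct the interval, but they recover less power than a model with a participant term.

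Recompute the detectable increase for N = 100 under that model from the coffee-study daily counts. Report the mean, the within-person variance or dispersion and the adjacent-day correlation used, and say whether 2% is relative. Restate the figure in section 10.1 and the synopsis only if it is not confirmed.

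The cost is one sentence and one recalculation, with no change to the design. The estimate becomes a within-person rate ratio in place of a ratio of overall mean counts, people with no ectopy on any day add no information, and the stated detectable increase may turn out less favourable than 2%.

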10.2 Statistical Analysis Plan (SAP) and Outcome Assessment

Our primary analyses will employ intention-to-treat principles, examining randomization assignment as the primary predictor. Secondary analyses will examine "per-protocol" compliance, which will also allow for quantitative assessments of outcomes per the number of hours off hypoglossal stimulation as the predictor. We will employ logistic regression with robust standard errors (to take clustering within individuals into account) for the dichotomous presence or absence of outcomes (such as at least one daily PAC, PVC, or episode of AF), and a negative binomial model to assess number of daily events.

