10.3 Intention-to-Treat (ITT)

The main intention-to-treat (ITT) analysis set will include all randomized participants, whether they are compliant with the treatment allocation for this trial or not. Every

attempt will be made to collect data until the end of the follow-up period for all randomized participants and these data will be included as part of the main ITT analysis. The analyses for the primary objective will be performed using the ITT dataset.

Although substantial crossover is not anticipated, as treated analyses will also be conducted if failure to comply with allocated treatment assignments occurs in more than 10% of cases or if there is a significantly different proportion of assignment adherence for "ON" versus "OFF" HGNS use.

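### The hours-off, per-protocol and as-treated analyses rest on self-selected device use and can show a false effect of about the 2% target size; the primary ITT analysis is unaffected

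*Protocol*

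**What the plan says.** Section 10.2 makes randomised assignment the primary predictor. It then plans secondary per-protocol analyses, which are also to provide "quantitative assessments of outcomes per the number of hours off hypoglossal stimulation as the predictor". No condition is attached to these.

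Section 10.3 keeps every randomised participant in the ITT set and uses that set for the primary objective. It adds as-treated analyses under either of two conditions. The first is a threshold on overall non-adherence: "if failure to comply with allocated treatment assignments occurs in more than 10% of cases". The second compares the on and off assignments and applies "if there is a significantly different proportion of assignment adherence".

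Three other places matter:
- Section 3.1 describes the trial as non-blinded.
- Section 8.3 acknowledges that, in ordinary care, patients sometimes leave the device off, with comfort given as an example.
- Section 10.1 ties the power statement to ITT alone: "80% power in intention-to-treat analyses comparing nights on and off HGNS to detect a 2% increase in cardiac ectopy".

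**The concern.** Device use on a given night is a post-randomisation exposure. A night that is bad for reasons unrelated to the assignment (illness, discomfort, broken sleep) may shorten use on an assigned-on night. It may also raise ectopy by itself: the trial's own hypothesis in Section 2.1 is that disrupted sleep does so. Grouping nights by actual use, dropping non-compliant nights, or regressing ectopy on hours off then attributes the bad night to the missing stimulation.

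These are the only compliance-based and dose-related results the protocol describes, and the effect sought is small. Modest confounding could produce an apparent effect of similar size, which readers might take as support for a causal dose-response.

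**Working it through.** **The plan's own figure.** Section 10.1 states 100 participants, 80% power, two-sided alpha 0.05 and a 2% increase. It names a source ("Based on the frequencies that cardiac ectopy observed among 100 healthy individuals") but gives no SD, dispersion or rate, so the figure can only be back-solved. The required standard error of the log ratio is log(1.02)/(1.960 + 0.842) = 0.0198/2.802 = 0.0071. With 100 participants, this implies an SD of about 0.071 for the within-person mean log difference. That neither confirms nor refutes the figure. The 2% serves here only as a yardstick.

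**Nights.** Section 7.8 says "participants will be randomized in pairs of either" on-off or off-on, so 14 nights give 7 on and 7 off per participant, or 700 against 700 in total.

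**Assumed inputs (none in the protocol).** The true device effect is zero. A share b = 0.20 of nights is bad, with ectopy r times that of other nights. A share s_on of on nights, all bad, is spent off. A share s_off of off nights is spent on. The mean in each assigned arm is m = 1 - b + br, so the ITT ratio is m/m = 1.

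**As-treated**, with x = r if the switched off nights are bad and x = m if they are random:
- mean of nights actually off = (m + s_on·r - s_off·x)/(1 + s_on - s_off)
- mean of nights actually on = (m - s_on·r + s_off·x)/(1 - s_on + s_off)

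For r = 1.10, s_on = 0.10, s_off = 0: m = 1.02; off = (1.02 + 0.11)/1.10 = 1.0273; on = (1.02 - 0.11)/0.90 = 1.0111; ratio 1.016.

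**Per-protocol** (switched nights dropped), r = 1.10: 1.02/1.0111 = 1.009.

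**Hours-off slope.** Suppose regular on nights have 0 h off (weight 0.4), bad on nights 3 h (0.1) and off nights 7 h (0.5). Mean hours = 3.8; variance = 0.9 + 24.5 - 14.44 = 10.96; covariance with log ectopy = (0.3 + 0.7 - 0.76)·log r = 0.24·log r. Over 7 hours the slope is 7 × 0.24/10.96 = 0.153·log r.

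| False effect, true effect zero | r = 1.10 | r = 1.20 |
|---|---|---|
| As-treated, 10% of on nights switched | +1.6% | +3.2% |
| As-treated, same plus 5% of off nights at random | +1.6% | +3.1% |
| Per-protocol, 10% of on nights dropped | +0.9% | +1.7% |
| Hours-off slope over 7 h | +1.5% | +2.8% |
| As-treated, 5% of on nights switched | +0.8% | +1.6% |
| As-treated, 10% switched in each arm, all bad | 0.0% | 0.0% |
| As-treated, 10% of off nights switched on, all bad | -1.6% | -3.1% |
| ITT | 0 | 0 |

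The r at which the as-treated bias reaches 2% is 1.13 with 10% of on nights switched (1.15 if 30% of nights are bad), 1.26 (1.31) with 5%, and 1.06 (1.07) with 20%.

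**Simulation** (1,000 runs, 100 participants, 14 nights, randomised in pairs). ITT bias lay between -0.1% and +0.1%. With 10% of on nights switched and r = 1.1 to 1.2, as-treated and hours-off estimates were about +1.4% to +3.9%. With r = 1.2, no switching, and 2 h of use lost on bad on nights, the within-person hours-off estimate was still +1.7%. Switching unrelated to the night or the person gave no bias. When high-ectopy participants switched off more often (about 6% of on nights, r = 1), an as-treated model without participant effects gave +7.1%, against 0.0% within participant.

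**Trigger.** With 10% of on nights and 5% of off nights non-adherent, overall non-adherence is 7.5%, below the 10% rule. The gap of 95% against 90% gives z = 0.05/√(0.925 × 0.075 × 2/700) = 3.55, so the second condition fires. A gap of 95% against 92.4% gives z = 2.0. Both calculations ignore clustering.

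**The case against.** The strongest reply is that the primary inference is protected. ITT is kept whatever adherence turns out to be, the as-treated analysis is an addition, and the per-protocol and hours-off work is labelled secondary. All of that stands.

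The trigger can also be defended. It is prespecified, it looks at adherence and not at ectopy, and with little crossover an as-treated analysis would nearly repeat ITT. A reader might infer that results are being selected by outcome, or that all the compliance analyses are conditional. The protocol supports neither: only the as-treated analysis has a trigger.

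A reader might also infer that the trigger fires precisely when non-adherence is informative. It does not test that. Differential adherence can be harmless, and symmetric informative switching produced no as-treated bias. What remains is narrower: a significant on/off adherence gap is one setting in which this bias can arise.

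The magnitude rests on assumptions. The protocol gives no adherence rate, share of bad nights or ectopy ratio, does not define hours off operationally, and expects little crossover. The positive figures need switching concentrated in bad on nights. This objection stands and limits the claim to what could happen.

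Finally, estimators and labels for secondary analyses are often left to a SAP, which is not shown. But the protocol itself fixes hours off as a predictor and sets the as-treated rule, so the point can be raised on this document.

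**Conclusion.** The concern holds as a cheap improvement to the secondary analyses. Sections 10.2 and 10.3 prescribe analyses on achieved use, which participants partly choose. With a true effect of zero, 20% bad nights, 10% of on nights switched off (all bad) and 10-20% more ectopy on bad nights, they give about +1% to +3%, comparable to the 2% target. With 5% switching, or ectopy only about 5% higher on bad nights at 10% switching, the bias is mostly below 2%. It is zero under symmetric switching and negative under reverse switching.

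A reader might conclude that the trial's main result is at risk or that a false positive is to be expected. Neither follows: ITT is unbiased in every scenario examined, and the size and sign of the bias depend on inputs the protocol does not give.

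**What to change.** In Sections 10.2 and 10.3:
1. Report, whether or not the as-treated trigger fires, one within-participant adherence-adjusted estimate beside ITT, using randomised assignment as the instrument for device use. Give it for use yes/no and for hours of use under an assumed linear effect; a control-function count model is one way to fit it.
2. Label the raw hours-off, per-protocol and as-treated results exploratory and non-causal.

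No new data are needed: Section 6.3 already collects daily device reports, and assignment is known for every night.

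The costs are modest. With a net adherence contrast of 85-90%, the interval is 1/0.90 = 1.11 to 1/0.85 = 1.18 times as wide as that of ITT. The estimate assumes that assignment affects ectopy only through device use, which deserves discussion in an unblinded trial, and that the effect is linear in hours. It essentially rescales the ITT contrast, so it says nothing about the shape of a dose-response. The hours-off analysis can stay for that purpose, as description.

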1 INTRODUCTION

1.1 BACKGROUND

Sleep disorders and poor sleep are a major public health problem owing to their prevalence and adverse effects. One health condition that sleep disorders have long been implicated in is the development of AF. AF is the most common sustained cardiac arrhythmia. In a recent study, we estimated that the current US national prevalence of diagnosed AF is at least 10.55 million, comprising 4.48% of the adult population, substantially exceeding prior projections. AF is a leading cause of stroke, reduces quality of life, increases risks of myocardial infarction and dementia, and results in > \$28 billion in US healthcare expenditures annually.

The relationship between poor sleep and incident AF was initially attributed to a common association with obstructive sleep apnea (OSA). However, emerging evidence suggests that chronic sleep disruption independent of OSA may play a role in the development of AF. Indeed, work largely from our group has revealed that abnormal sleep characteristics including frequent nighttime awakening, less rapid eye movement (REM) sleep, and a diagnosis of insomnia may predict incident AF, even after adjustment for OSA.^{4,5} Furthermore, studies of the circadian variation of arrhythmia onset patterns in patients with AF have shown a nocturnal predominance, suggesting that nocturnal events such a disrupted sleep may be arrhythmogenic.^{6,7} Whereas the available evidence mostly support chronic sleep disruption as a risk factor for incident AF, less is known about the near-term risk of a discrete AF episode following a night of disrupted or poor-quality sleep.

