2.2 Specific Objectives

- Primary:
 - To assess the effect of sleep disruption on daily number of cardiac ectopic beats.
- Secondary:
 - o To assess the effect of sleep disruption on daily number of PACs.
 - o To assess the effect of sleep disruption on daily number of PVCs.
 - To assess the effect of sleep disruption on the daily presence versus absence of AF.

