5 PARTICIPANT SELECTION

5.1 Inclusion Criteria

Participants must meet all the following to be eligible:

- Are age 21 years or older
- Have a HGNS device implanted for OSA and followed up at UCSF
- Are willing to abstain from using the upper airway stimulation device for no more than two consecutive days as instructed over the 14-day trial period
- Able and willing to provide written informed consent

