8.2 Benefits

There are no direct benefits for participating in this study. However, the knowledge gained from this study may help better understand the mechanisms underlying AF occurrence. Furthermore, compelling evidence of the direct impact of sleep disruption on discrete AF episodes would be directly and immediately relevant to clinical care of patients with AF.

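### The secondary AF comparison rests on however many participants have AF, probably few, and the robust-SE logistic model in 10.2 is unreliable at such numbers

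*Protocol*

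**What the plan says.** Section 2.2 lists as a secondary objective "To assess the effect of sleep disruption on the daily presence versus absence of AF". The synopsis defines the endpoint as AF episodes of at least 30 seconds, scored present or absent each day. Section 10.2 fixes the model: "We will employ logistic regression with robust standard errors (to take clustering within individuals into account) for the dichotomous presence or absence of outcomes", and names an episode of AF as one such outcome. It mentions no small-sample provision.

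The disease-related entry criterion in 5.1 is "Have a HGNS device implanted for OSA and followed up at UCSF"; AF is not required. Section 5.2 excludes users of class 1 or 3 antiarrhythmics. The synopsis also excludes permanent or continuous AF, but 5.2 does not, and the two lists need reconciling.

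Under 7.8, days are randomised in pairs, off-on or on-off, which gives 7 off and 7 on days to a participant who completes 14 days. The sample size in 10.1 is "to detect a 2% increase in cardiac ectopy" and gives no figure for AF. The only AF frequency in the protocol is in 1.1: "the current US national prevalence of diagnosed AF is at least 10.55 million, comprising 4.48% of the adult population".

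**The concern.** Clustering on participant suggests 100 independent units. For AF that is misleading. A participant with no AF day has the same outcome on off and on days and carries almost no information about the difference. If only a few people have AF, the sandwich variance is estimated from those few, and a normal reference treats it as if it were well estimated.

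The stake is how the AF result is read. Section 8.2 says that "compelling evidence of the direct impact of sleep disruption on discrete AF episodes would be directly and immediately relevant to clinical care". A nominally significant AF odds ratio could come from two or three people and still carry a p-value that looks like evidence from 100.

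**Working it through.** **The plan's own figure.** There is none for AF. The stated 80% power for a 2% rise in ectopy at N = 100 implies, by the paired normal approximation on the log ratio, SD = ln(1.02) × √100 / (1.960 + 0.842) = 0.0198 × 10 / 2.802 = 0.071. No SD or dispersion is given, so this can be neither confirmed nor refuted, and it says nothing about AF.

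**How many participants might have AF.** At 4.48%, the expected number is 100 × 0.0448 = 4.5, with a central 95% binomial range of 1 to 9. This borrows a national figure for diagnosed AF. The protocol gives none for this cohort.

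**Why the others add nothing.** With 100 participants and 7 days per condition, let p1 and p0 be the overall proportions of off and on days with AF. A participant with s1 off and s0 on AF days contributes to the log odds ratio

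u = (s1 − 7p1) / [700 p1(1 − p1)] − (s0 − 7p0) / [700 p0(1 − p0)],

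and the sandwich variance is the sum of u², times 100/99. As an illustration, take five participants with off/on AF days of 4/1, 3/1, 2/2, 1/1 and 0/1, so p1 = 10/700 and p0 = 6/700. Their u values are 0.238, 0.136, −0.133, −0.067 and −0.168, and their squares sum to 0.126. Each of the other 95 has u = −0.000058, and their squares sum to 0.0000003. The variance comes from five people.

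**False-positive rate under no effect.** I simulated 40,000 trials per setting with a Wald test at 1.96. Trials with no AF day in one condition count as not rejecting. K is the number of AF-prone participants. Even means the same daily risk for each; uneven means risk drawn from a beta distribution with parameters summing to 2. K, the AF-day frequency and its spread are all assumptions.

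| K | AF on 10% of days: even / uneven | AF on 30% of days: even / uneven |
|---|---|---|
| 3 | 8.9% / 23.2% | 22.4% / 25.1% |
| 5 | 8.1% / 22.7% | 13.7% / 15.5% |
| 10 | 7.2% / 15.6% | 8.6% / 8.6% |
| 20 | 6.0% / 9.5% | 6.7% / 6.5% |

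The largest value found was 26.6% (K = 3, uneven, 25% of days). With 10% of days and uneven spread, no estimate existed in 45% of trials at K = 3 and 25% at K = 5.

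**Sparse, even AF.** At 5% of days the rate is 3.1% to 3.2% for K = 3 to 10, with no estimate in 57% (K = 3), 31% (K = 5) and 5% (K = 10) of trials. At 2% of days it is about 0.5%, with no estimate in 74% (K = 5) and 43% (K = 10).

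**Alternatives in the same settings.** The exact within-pair test rejected in at most 3.7% of null trials. The same odds ratio and robust SE, referred to t with (participants with any AF − 1) degrees of freedom, rejected in at most about 5.5%.

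**Power of a valid test.** At a true odds ratio of 2, with AF on 20% of on days (even) or a mean of 25% (uneven), either alternative has about 9% to 16% power at K = 5 and 21% to 36% at K = 10.

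**The case against.** Four objections have weight.

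- **The number with AF is unknown.** The 4.48% is a stated minimum for diagnosed AF in all US adults. These are patients with obstructive sleep apnoea, which 1.1 itself links to AF, and a continuous patch also records undiagnosed episodes. A reader might infer that only a handful can inform the endpoint; the protocol does not establish that. With 20 AF-prone participants the inflation is modest. This stands and makes the point conditional.
- **The direction is not fixed.** A reader might infer that the model always rejects too often. With sparse, even AF it rejects too rarely or gives no estimate. It is also tempting to quote rates among estimable trials only: 30% for K = 5, 10% of days, uneven. That figure needs very uneven burden and leaves out the quarter of trials with no estimate; over all trials it is 23%.
- **The protocol does not claim power for AF.** AF is secondary, 2.1 puts the hypothesis in terms of PACs and PVCs, and 1.2 explains that ectopy was chosen because everyone has it. The sentence in 8.2 is conditional. Nothing says a null AF result would be read as evidence against triggering, so that charge and a rewrite of 8.2 are not supported.
- **A correction may be in an analysis plan that is not shown.** If a small-cluster reference is specified there, the point is met. But 10.2 does name the model for AF, and as written the natural reading is the usual Wald test.

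**Conclusion.** The point holds in conditional form. The AF comparison in 10.2 effectively rests on the participants who have AF, and that number is not planned for and is probably small. With an uncorrected Wald test, 3 to 10 such participants and AF on 10% to 30% of their days, the false-positive rate is roughly 7% to 27% of all trials, depending on how unevenly AF is spread. With 20 it is about 6% to 10%. With sparse, even AF it is below 5%, often with no estimate when few participants are AF-prone. The stated method is therefore unreliable in either direction, rather than uniformly anti-conservative. The conclusion assumes complete 7 versus 7 follow-up, no small-sample correction and the burden distributions shown. It concerns one secondary endpoint. The ectopy analysis, to which every participant can contribute, is not affected.

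**What to change.** In 10.2, for daily AF presence, specify one of two methods:

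- an exact within-pair test that follows the randomisation in 7.8: among randomised pairs with AF on exactly one of the two days, test off versus on against 1/2; or
- the logistic odds ratio and robust SE already planned, referred to a t distribution with degrees of freedom equal to the number of participants with any AF minus 1, and no test if only one participant has AF.

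Report the number of participants with any AF and the number of discordant pairs, and label the AF comparison exploratory.

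The cost is wording only, with no new data or participants. The exact test is conservative (size at or below about 4%) and gives no population-averaged odds ratio. The t version keeps the odds ratio and an interval but still fails when one condition has no AF day. Either way the AF claim becomes more modest, which the low power above warrants.
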